#### Safety parameters definitions

- 1) A TEAE (Treatment-Emergent AE) is defined as an AE that meets either of the following conditions:
  - Begins on or after the first instillation of investigational medical device on D0;
  - Begins before D0 and worsens in severity on or after the first instillation of investigational medical device on D0.
- 2) A DD (Device Deficiency) is an inadequacy of the investigational medical device related to its identity, quality, durability, reliability, safety or performance. This may include malfunctions, use error, or inadequacy in the information supplied by the manufacturer.  
It will be detected by any answer "YES" to the question "Has there been a deficiency of the medical device?".
- 3) An ADE (Adverse Device Effect) is an adverse event related to the use of an investigational medical device.  
It will be detected by any answer "YES" to the question "Has there been a deficiency of the medical device?" followed by an answer "YES" to the question "Has this led to an adverse event?".

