6.2 Definition of Adverse Device Effect

Information about every adverse device effect (ADE) will be collected and recorded.

Adverse event related to the use of an investigational medical device.

NOTE 1- This includes any adverse event resulting from insufficiencies or inadequacies in the instructions for use, the deployment, the implantation, the installation, the operation, or any malfunction of the investigational medical device.

NOTE 2- This includes any event that is a result of a use error or intentional abnormal use of the investigational medical device.

The Investigator is obliged to determine the severity of the event and evaluate the causal relationship of the event to the investigational medical device.

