6.4 Definition of Serious Adverse Device Effect

Information about every serious adverse device effect (SADE) will be collected and recorded.

Adverse device effect that has resulted in any of the consequences characteristic of a serious adverse event.

6.5 Definition of Unanticipated Serious Adverse Device Effect and Anticipated Serious Adverse Device Effect

Information about every Unanticipated Serious Adverse Device Effect and Anticipated Serious Adverse Device Effect (ASADE) will be collected and recorded.

Serious adverse device effect which by its nature, incidence, severity or outcome has not been identified in the current version of the risk analysis report is considered as an unanticipated serious adverse device effect (USADE).

An anticipated serious adverse device effect (ASADE) is an effect which by its nature, incidence, severity or outcome has been identified in the risk analysis report.

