6.6 Definition of Device Deficiency (DD)

Information about Device Deficiency (DD) will be collected and recorded.

Inadequacy of an investigational medical device related to its identity, quality, durability, reliability, safety or performance. This may include malfunctions, use error, or inadequacy in the information supplied by the manufacturer.

Device Deficiency that might have led to a SAE if:

- a) suitable action had not been taken or
- b) intervention had not been made or
- c) circumstances had been less fortunate

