- the event has a temporal relationship with investigational device use/application or procedures;
- the event involves a body-site or organ that
 - . the investigational device or procedures are applied to;
 - . the investigational device or procedures have an effect on;
- the event follows a known response pattern to the medical device (if the response pattern is previously known);
- the discontinuation of medical device application (or reduction of the level of activation/exposure) and reintroduction of its use (or increase of the level of activation/exposure), impact on the event (when clinically feasible);
- other possible causes (e.g. an underlying or concurrent illness/ clinical condition or/and an effect of another device, drug or treatment) have been adequately ruled out;
- harm to the subject is due to error in use.

In order to establish the relatedness, not all the criteria listed above might be met at the same time, depending on the type of device/procedures and the event.

Related adverse events (including serious adverse events) are AEs with at least a possible relationship to the investigational medical device or procedure.

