## 4 MODIFICATIONS FROM THE STATISTICAL SECTION OF THE PROTOCOL

Descriptive analysis will be provided by center for the primary performance endpoint (ocular surface staining) and for the global sum score of dry eye symptoms. Centers with less than 4 subjects will be pooled.

If a center seems to be an outlier with non-homogeneous data compared to other centers, additional analyses will be performed excluding the center to support the main results.

Descriptive analysis on the percentage of patients with an ocular surface staining score = 0 will be performed on D28 and D90.

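### SAP 6.3 detects an adverse device effect only through a reported device deficiency, so a related adverse event without one is not counted in the ADE rows

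*SAP*

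**What the plan says.** Protocol 6.2 defines an ADE as an "Adverse event related to the use of an investigational medical device" and asks the investigator to judge causality. Its NOTE 1 widens the definition: "This includes any adverse event resulting from insufficiencies or inadequacies in the instructions for use", and it goes on to malfunction. Protocol 6.7 sets the threshold: "Related adverse events (including serious adverse events) are AEs with at least a possible relationship to the investigational medical device or procedure".

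Device deficiency is defined separately in Protocol 6.6: "Inadequacy of an investigational medical device related to its identity, quality, durability, reliability, safety or performance".

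Protocol 6.4 defines a serious ADE as an "Adverse device effect that has resulted in any of the consequences characteristic of a serious adverse event". Protocol 6.5 splits serious ADEs into anticipated and unanticipated; an unanticipated one "has not been identified in the current version of the risk analysis report".

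SAP 6.3, safety parameters definitions, item 3, repeats the Protocol 6.2 definition. It then gives one detection rule: a YES to the question on a "deficiency of the medical device?' followed by an answer 'YES' to the question 'Has this led to an adverse event". It offers no route through the causality assessment. SAP 7.7.4 describes all the adverse event variables and compares them between groups.

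**The concern.** The detection rule does not carry out the definition in the sentence before it. Take a reaction that the investigator rates as probably related to the drops, with no deficiency recorded. Under the Protocol it is an ADE. Under the SAP rule it is not.

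Assessing safety is one of the primary objectives (Protocol 1.0). In the all-body block of SAP 6.3, only the ADE-labelled rows are meant to show relatedness. Across all three blocks, only the ADE-labelled rows are meant to show events that are both serious and related. If those rows depend on a deficiency tick, the report could show few or no ADEs beside a larger count of treatment-emergent events (TEAEs) related to the eye drops. SAP 7.12 imputes a missing causality as probably related, but that safeguard never reaches the ADE rows, because the ADE rule does not use causality.

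**Working it through.** The plan states no figure to reproduce on this point. The check has three parts: compare the rules, count the rows, and illustrate how the count behaves.

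**1. The rules side by side**

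| Event starting after the first instillation | Protocol 6.2 and 6.7 | SAP 6.3 item 3 |
|---|---|---|
| Causality to the product possible or higher, no deficiency reported | ADE | not counted |
| Causality possible or higher, deficiency reported as its cause | ADE | counted |
| Causality unlikely or not related, deficiency reported as its cause | ADE through NOTE 1 of 6.2 | counted |
| Causality unlikely or not related, no deficiency | not an ADE | not counted |

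The two disagree in the first line only. The third line matters for the fix: a rule using causality alone would move the disagreement there.

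**2. Rows in SAP 6.3** (yes/no adverse event rows; free-text descriptions excluded)

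| Area | All rows | Plain ADE | Serious, unanticipated serious and anticipated serious ADE | Rows using causality |
|---|---|---|---|---|
| All body | 8 | 1 | 3 | 0 |
| Ocular | 10 | 1 | 3 | 2 |
| Non-ocular | 10 | 1 | 3 | 2 |
| Total | 28 | 3 | 9 | 4 |

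- Rule applied directly: 3/28 = 10.7%.
- Rule probably inherited: 9/28 = 32.1%.
- Rows using causality: 4 (TEAEs related to the eye drops, and to the procedure, in two areas). None is all-body.
- Serious rows: 5 per area × 3 areas = 15, of which 9 are ADE-labelled and 15 − 9 = 6 are serious AE or serious TEAE. Rows that combine seriousness with causality: 0.

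These are shares of table rows, not of subjects.

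**3. How the count behaves** (illustration; the inputs are assumed, not taken from the documents)

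Suppose 10 subjects have a related adverse event, and a share s of them also has a deficiency recorded as its cause. The Protocol definition counts 10 and the SAP rule counts 10 × s:

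- s = 0 gives 0
- s = 0.1 gives 1
- s = 0.5 gives 5
- s = 1 gives 10

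The documents give neither the number of related events nor s, so the actual shortfall cannot be stated.

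**The case against.** The strongest reply is that most of the wanted analysis is already planned. The ocular and non-ocular blocks each have a row for TEAEs at least possibly related to the eye drops, at the Protocol 6.7 threshold and compared between groups. Protocol 7.6.1 also plans a TEAE summary by relationship, and SAP 7.7.4 lists every adverse event. This stands, and it limits the point. A reader might infer that related events vanish from the safety report; they do not. The reply does not cover the all-body view or seriousness combined with relatedness.

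A second reply is that deficiency is defined broadly enough, safety and performance included, for a site to record a reaction as one. Protocol 4.6 names local allergic reactions as a known risk, and such a reaction might or might not be ticked. This also stands: the mismatch in the rule is certain, but a practical undercount is not shown. It would still leave the ADE count dependent on how each site reads the deficiency question, although causality is assessed for every event (Protocol 6.8).

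Third, the effect on the 9 serious-type rows is an inference. Protocol 6.4 and 6.5 define those categories within ADE and the SAP gives them no other rule. They also say that information on each category will be recorded, so it may be captured directly on the eCRF.

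Finally, a reader might infer an undeclared change, because SAP section 4 does not mention the narrower rule. The documents do not support that. Section 4 is headed "MODIFICATIONS FROM THE STATISTICAL SECTION OF THE PROTOCOL", whereas the ADE definition sits in Protocol section 6, and the statistical section plans no ADE analysis.

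**Conclusion.** The point holds as an internal inconsistency in SAP 6.3: the detection rule is narrower than the definition it serves and than Protocol 6.2 and 6.7. It affects 3 rows directly and probably 9 more, out of 28. The second figure assumes that the serious-type ADE rows are derived from the ADE flag.

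The real loss lies in the all-body ADE row, in any row meant to show events as both serious and related, and in consistency between the ADE rows and the related-TEAE rows. The stated safety endpoints (TEAE rates and visual acuity), SAE reporting, the adverse event listings and the primary analysis are unaffected. The documents do not support a claim that safety signals would be hidden, nor any estimate of how many subjects would be misclassified.

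**What to change.** Replace the detection rule in SAP 6.3 item 3. Count as an ADE any adverse event with onset or worsening no earlier than the first instillation of the assigned investigational product that meets **either** condition:

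- causality to that product is possible, probable or certain, after the SAP 7.12 imputation; or
- it is recorded as led to by a deficiency of that product (Protocol 6.2 NOTE 1).

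Three details matter:

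- **Both arms of the rule are needed.** With causality alone, a deficiency-led event coded unlikely or not related would drop out, against NOTE 1.
- **The timing limit is an addition to Protocol 6.2.** Adverse events are collected from consent (Protocol 4.3), so without it a run-in event with missing causality would be imputed as related to a product not yet given.
- **The product must be named.** SAP 6.3 also tabulates deficiencies of the run-in tears, and Protocol 6.7 relatedness also covers procedures.

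Derive the serious, unanticipated serious and anticipated serious ADE rows from this set, using seriousness and the risk analysis report. Show deficiency-led events also in a separate row, and query any coded unlikely or not related.

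The cost is SAP wording and one derivation, using causality (Protocol 6.8) and serious ADE information (Protocol 6.4 and 6.5) that are already to be collected. Reported ADE counts may rise, and the ocular and non-ocular ADE rows will largely overlap the existing related-TEAE rows.

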#### 6.4 Concomitant treatments

Topic	Area	Analyzed parameters	Time of evaluation
Concomitant treatments	Ocular	- Treatment description during the study	During all study
Concomitant treatments	Non-ocular	- Treatment description during the study	During all study
Change concomitant treatments	-	- Change in concomitant treatments Yes/No	D0 / D7 / D28 / D90

## 6.5 Compliance and exposure to treatment

Analyzed parameters	Description	Time of evaluation
Compliance evaluated by the investigator		
Diary returned by the patient	Yes / No	D0 / D28 / D90
After review of the subject's diary, has the patient compliance been good?	Yes / No	D0 (ART) / D7 / D28 / D90
Exposure and compliance to ART		
Exposure to ART	Number of ART days between the first ART instillation (date of the screening visit D-14) and the last ART instillation (as collected at D0 in the eCRF)	Between D-14 and D0
Average daily ART administration	Total number of ART administrations (as specified in the Diary A excluding the day of the visits Screening and D0) / Number of completed days in the Diary A excluding the day of the visits Screening and D0	Between D-14 and D0
% of days with at least one instillation	If the number of filled days $\geq$ 3/4 of the interval between D-14 and D0: 100 x Number of days with at least one ART instillation (Diary A) / Number of filled days in Diary A	Between D-14 and D0
Exposure and compliance to treatment		
Exposure to treatment	Number of treatment days between the first investigational drop instillation (date of baseline D0) and the last investigational drop instillation (as collected at the end of the study in the eCRF)	Between D0 and D90 or end of study
Average daily investigational drop administration	Total number of ART administrations (Diaries B+C excluding the day of the visits D0 and D90 or end of study) / Number of completed days in the Diaries B+C excluding the day of the visits D0 and D90 or end of study	Between D0 and D90 or end of study
Compliance at D28	If the number of filled days $\geq$ 3/4 of the interval between D0 and D28: 100 x Number of days with 3 to 6 treatment administrations (Diary B excluding the day of the visits D0 and D28 or end of study) / Number of filled days in the diary B (excluding the day of the visits D0 and D28 or end of study)	Between D0 and D28 or end of study
Global compliance	If the number of filled days $\geq$ 3/4 of the interval between D0 and D90/End of study: 100 x Number of days with 3 to 6 treatment administrations (Diaries B+C Excluding the day of the visits D0 and D90 or end of study) / Number of filled days in the diary B+C (excluding the day of the visits D0 and D90 or end of study)	Between D0 and D90 or end of study

## 6.6 Tolerability and ease-of-use

Analyzed parameters	Description	Time of evaluation
Upon instillation, these eye drops are comfortable in my eyes	Strongly agree / agree / disagree / Strongly disagree	Diary D7 / D28 / D56 / End of last week or day before D90
The bottle is easy to use	Strongly agree / agree / disagree / Strongly disagree	Diary D28 / End of last week or day before D90
I can instill exactly one drop with this bottle	Strongly agree / agree / disagree / Strongly disagree	Diary D28 / End of last week or day before D90

## 6.7 Other variables: Dates and Time intervals

Analyzed parameters	Description	Time of evaluation
Number of days between visits	Computed with the dates of visits	D0 / D7 / D28 / D90
Duration in the study	Computed with the dates of visits	D90 or End of study
Date of first visit	Computed with the dates of visits	D-14
Date of last visit	Computed with the dates of visits	D90 or End of study

## 6.8 End of study

Analyzed parameters	Description	Time of evaluation
Has the patient completed the study until D90?	Yes / No	End of study
Premature withdrawal: Screened patients (not randomised)		
Main reason for premature end of study	- Patient ineligible at visit D-14 - Patient ineligible at visit D0 - Other	End of study
Premature withdrawal: Randomised patients		
Last visit	D0/D7/D28/D90	End of study
Main reason for premature end of study	- Non compliance - Investigator's decision - Non-medical reason - Adverse event leading to study exit - Lost to follow-up - Consent withdrawn - Other	End of study

## 7 STATISTICAL ANALYSIS

### 7.1 Software documentation

Statistical analyses will be performed with SAS® version 9.4 or higher (SAS institute, North Carolina, USA).

### 7.2 General approach

Quantitative variables will be summarized into count of non-missing data, mean, standard deviation, minimum, maximum, median and, if necessary, 95% confidence interval of the mean.

Categorical data will be described into count and percentage with 95% confidence interval if necessary.

All statistical analyses will be performed at the 5% significance level using 2-sided test or 2-sided confidence intervals if necessary.

Normality will be tested by the Shapiro-Wilk at the 1% threshold.

### 7.3 Disposition of patients

The disposition of patients will be displayed on a flow-chart.

A table will present the number and percentage of patients by treatment group for each population and at each visit.

Reasons of exclusion from the study and protocol deviations (major and minor) will be described.

Study discontinuations and reasons will be listed by group.

### 7.4 Screening and baseline characteristics

Baseline characteristics will be described by treatment group on the ITT, PP and Safety populations.

For data collected on both eyes, the description will be performed on the study eye and fellow eye separately (calculations unit = 1 eye). As defined by the protocol; the study eye is the eligible eye with the highest total ocular surface fluorescein staining score at baseline or, if both eyes are eligible and have the same score, the study eye is the right eye.

Dry eye history as well as ocular and non-ocular history will be described in each group.

Visual acuity at baseline will be described by class for each treatment group:  $\geq 8/10$ , [5/10 1 8/10[, [1/10 - 1/10[ and < 1/10.

Ocular prior treatments will be described in each group by classes defined as follows: Carbomer, Cellulose derivatives, Hyaluronic acid, Hydroxypropyl-guar gel, Hydroxypropyl-guar gel & Lipid emulsion, Lipid emulsion, Osmoregulator, Osmoregulator & Hyaluronic acid, Other, Vinyl polymer, Vit A ointment.

Non-ocular prior treatments will be described in each group by defined therapeutic classes (first ATC level: A, B, C, D, G, H, J, L, M, N, P, R, V).

All adverse events before investigational treatment administration will be described in each group by MedDRA'S « System Organ » and « Preferred Term ».

In addition, a brief description will be provided for patients with screening failure as well as if any AE was recorded during the screening period.

## 7.5 Primary performance endpoint analysis

The primary performance endpoint is the mean CFB in the study eye at visit 4 (D28  $\pm$  3 days) in ocular surface fluorescein staining score, combining corneal, nasal and temporal bulbar conjunctival fluorescein staining score, each graded from 0 to 5, according to the Oxford scheme.

The primary performance endpoint analysis will be performed on the per-protocol population.

The primary performance endpoint will be analyzed by an analysis of covariance including the treatment as fixed effect and the baseline ocular surface staining score as covariate (SAS® Mixed procedure). The two-sided 95% confidence interval for the difference [CBL-102 Eye Drops: D28-D0] – [Vismed Multi: D28-D0] will be computed by the model. The non-inferiority will be demonstrated if the upper bound of the 95% CI is less than 2.

In addition to this model, and depending on the results of the baseline characteristics description, other relevant baseline covariates could be added to the model.

A sensitivity analysis including investigator site as covariate will also be performed using the same model. Mean CFB by treatment and by center will be displayed (if necessary, small centers will be grouped).

Summary statistics for continuous variables will be presented for the total ocular surface fluorescein staining score at D0, D28, and for CFB at D28 for each treatment group.

This analysis will also be performed on patients from the ITT population.

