7.6 Statistical Analysis

7.6.1 Methods of Analysis

Summaries for continuous variables will include the sample size (n), mean, standard deviation (SD), median, minimum, and maximum. Calculations will be based on the number of subjects (or eyes) with non-missing values for the study population being summarized.

Summaries for discrete variables will include frequencies and percentages. Percentages will be based on the number of subjects (eyes) with non-missing values. The denominator for percents will be the number of subjects (eyes) from the study population being analyzed. For each subject, baseline will be defined as the last non-missing measure prior to initiation of investigational treatment and endpoint will be defined as the measure of any follow-up scheduled visit. Change from baseline will be defined as (follow-up measure – baseline measure) and will be calculated if both baseline and follow-up endpoint are not missing.

The study eye will be the eligible eye with the highest total ocular surface fluorescein staining score at baseline or, if both eyes are eligible and have the same score, the study eye will be the right eye.

For each subject, the number of investigational eye drops used per day and for how many days during the course of study will be evaluated. It is expected that most subjects will not perform more than 6 applications per day on a continued regularly basis during the study.

The primary performance endpoint (mean change from baseline in total ocular surface fluorescein staining score) will be analyzed using analysis of covariance (ANCOVA) model. The model will include terms of treatment and baseline ocular surface staining score as covariates. Sensitivity analyses including investigator site as covariate will be performed. A 2-sided 95% confidence interval (CI) based on the ANCOVA model will be computed for the effect difference (CBL-102 Eye Drops *minus* Vismed® Multi). Non-

inferiority will be demonstrated if the upper bound of the 95% CI is less than 2 grades in the PP analysis. Supportive analysis of the primary endpoint will be performed on ITT population. The same ANCOVA model used to analyze the primary endpoint will be employed to analyze secondary continuous performance endpoints. Supportive analyses on secondary performance endpoints will be performed in the ITT and PP populations.

Ocular biomicroscopic assessment will be summarized at each visit using discrete summary statistics and presented by treatment.

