## 2 INTRODUCTION

The purpose of this analysis plan is to outline the statistical methods to be implemented during the statistical analysis of the data from the study CBL-2017-01: "A Study to Evaluate the Performance and Safety of CBL-102 versus Vismed® Multi Eye Drops in the Management of Dry Eye".

This analysis plan is applied to the protocol version 3 dated 25th of July 2017. Results obtained from the analyses outlined in this document will be the basis of the final report for this protocol. As with any statistical analysis plan, the proposed methods and approaches to the data analysis should be flexible. Changes to this plan may arise if ongoing analysis of the data suggests deviations from the original plan, considering that these changes would provide a more reliable and valid analysis of the data. Therefore, any deviations which occur from this plan will be adequately documented.

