### 7.13.3 Performance endpoints analyses

#### 7.13.3.1 Quantitative data (including primary endpoint)

➤ Global effects

Analyzed variable Type 3 Tests of Fixed Effects				
Effect	Num DF	Den DF	F Value	Pr > F
Group				
Value at baseline				
Other covariable				

➤ Model estimates

Analyzed variable					
CBL-102 Eye Drops LSMeans		Vismed Multi LSMeans		CBL-102 Eye Drops – Vismed Multi Difference of LSMeans	
Estimate (+/-SE)	95% CI	Estimate (+/-SE)	95% CI	Estimate (+/-SE)	95% CI

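### Does SAP 7.5 leave the non-inferiority decision open to covariates chosen after the baseline tables are seen?

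*SAP*

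**What the plan says.** Protocol 7.6.1 defines the primary analysis as an ANCOVA: "The model will include terms of treatment and baseline ocular surface staining score as covariates". It takes the two-sided 95% interval for the treatment difference from that model and declares non-inferiority if the upper limit in the per-protocol analysis is below 2 grades. The synopsis says the same.

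SAP 7.5 repeats the model, the interval and the rule in that order. After the rule comes the sentence at issue: "In addition to this model, and depending on the results of the baseline characteristics description, other relevant baseline covariates could be added to the model". The next paragraph reads "A sensitivity analysis including investigator site as covariate will also be performed using the same model", so the site model has a label that the covariate model lacks.

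Four other places bear on the point:

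- SAP 7.4: "Baseline characteristics will be described by treatment group on the ITT, PP and Safety populations".
- SAP 2 allows flexibility: "Changes to this plan may arise if ongoing analysis of the data suggests deviations from the original plan". The condition is that "these changes would provide a more reliable and valid analysis of the data", and deviations must be documented.
- SAP 4 lists the departures from the protocol's statistical section. None concerns the primary model.
- The results shell in SAP 7.13.3.1, which covers the primary endpoint, has a row for a further covariate.

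**The concern.** A confirmatory analysis should leave no choice of model once results can be seen. Here the possible covariates are unnamed, there is no limit on their number and no selection criterion, and the trigger is a table split by treatment group. The per-protocol version of that table cannot exist before Visit 4, because membership of that set depends on staying in the study until then. No sentence says in so many words that the two-term model alone decides.

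If the two-term and extended models gave upper limits on opposite sides of 2, an analyst might feel free to report the favourable one. The one-sided 2.5% risk of a false non-inferiority claim would then no longer be guaranteed.

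**Working it through.** **Step 1. Which model decides?**

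- Protocol 7.6.1 and the synopsis name one model with two terms, one interval from that model, and one rule applied to that interval.
- SAP 7.5 keeps this sequence. The optional covariates come only after the rule, and the sentence opens by presenting them as additional to the model already described. It therefore adds an analysis and replaces nothing.
- SAP 4 records additions as minor as descriptive tables by centre and the share of patients with a zero staining score. A new decision model would be a far larger departure, and it is not listed.
- The extra row in the 7.13.3.1 shell does not point the other way. The site-adjusted model needs such a row, and the same row appears in the 7.13.3.2 shell for qualitative data.

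**Step 2. The plan's own figures.** Inputs from Protocol 7.3: one-sided risk 0.025, power 0.90, margin 2, SD 2.5. The true difference is not stated, so I assume 0.

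n per arm = 2 × SD² × (z₀.₉₇₅ + z₀.₉₀)² / margin² = 2 × 6.25 × (1.960 + 1.282)² / 4 = 32.8, rounded up to 33, as stated. With 20% total loss, 33 / 0.8 = 41.25, rounded up to 42 per arm, or 84 in all, as stated.

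**Step 3. Does covariate choice on baseline data raise the risk?** I simulated trials with the true difference equal to the margin, so that every success is a false claim.

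- Taken from the plan: 33 per arm, SD 2.5, success if the upper 95% limit is below 2.
- Assumed: the baseline score explains 30% of the outcome variance; K independent further covariates each explain a share R²; a covariate enters if the arms differ on it at p < 0.10.
- Outcome = 2.5 × [√0.3 × baseline + √R² × (sum of covariates) + √(1 − 0.3 − K × R²) × noise] + 2 × treatment.
- 40,000 trials per row; Monte Carlo standard error near 2.5% = √(0.025 × 0.975 / 40,000) = 0.08 percentage points.

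| K | R² each | Two-term model decides | Imbalance-adjusted model decides | Success in either counts |
|---|---|---|---|---|
| 1 | 0 | 2.51% | 2.50% | 2.56% |
| 1 | 0.10 | 2.45% | 2.18% | 2.56% |
| 3 | 0 | 2.48% | 2.48% | 2.64% |
| 3 | 0.05 | 2.47% | 2.08% | 2.71% |
| 3 | 0.10 | 2.48% | 1.70% | 2.69% |
| 5 | 0 | 2.48% | 2.51% | 2.79% |
| 5 | 0.05 | 2.56% | 1.82% | 2.88% |
| 5 | 0.10 | 2.55% | 1.16% | 2.81% |

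A second simulation (20,000 trials per setting, 3 or 6 covariates correlated 0 to 0.3 with the outcome, entry at p < 0.20 or p < 0.05) gave 1.2% to 2.6% for the imbalance-adjusted model.

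The direction is what theory predicts. A covariate chosen from baseline data and allocation alone is chosen without regard to the outcome, so when it enters, the test remains valid. When it is left out, the arms happen to be close on it, so the fitted error variance overstates the uncertainty and the test is conservative.

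**Step 4. The conflict case.** The last column lets success in either model count. The largest excess over the two-term model is 2.88 − 2.56 = 0.32 percentage points.

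**The case for a change.** The strongest case for a change is that a favoured reading is not a stated rule. Other non-deciding analyses carry a label: the site model is a sensitivity analysis, the protocol calls the ITT analysis supportive, and SAP 7.6 gives secondary tests for information only. The covariate extension alone has none. SAP 6.1 lists many baseline variables, and SAP 2 does not expressly shield the primary decision from later changes. If an analyst could look at outcomes and keep the best model, the risk would rise. In the first simulation, allowing any one added covariate gave 2.8% to 3.3% with one candidate, 3.0% to 4.8% with three and 3.5% to 6.0% with five. The best of all models tried reached 7.4%.

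The missing label and the missing names stand. The larger figures carry little weight. They describe a search on the outcome, whereas the SAP ties the choice to baseline data. The 6.0% and 7.4% also need five covariates that explain 5 × 10% = 50% of the variance on top of the 30% assumed for the baseline score.

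Nor is it established that the choice would be made with Day 28 outcomes known. SAP 7.4 says how baseline data are displayed, not who picks covariates, when, or with what access to outcomes. Protocol 7.6.1 requires the SAP to be final before the codes are broken. SAP 2 treats later changes as deviations to be documented, so a switch of the primary model would be visible.

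**Conclusion.** The concern does not call for a change. Followed as written, the plan decides non-inferiority with the two-term ANCOVA in the per-protocol population, at a simulated risk of 2.45% to 2.56% against the nominal 2.5%. Adding covariates on baseline imbalance leaves the risk at or below nominal within simulation error (1.2% to 2.6%), and counting success in either model gives about 2.6% to 2.9%. These figures assume one to six independent covariates of modest strength and a fixed imbalance threshold, none of which the documents give. The unlabelled extended model is a gap in wording that an analyst reading the protocol and SAP together would fill by treating that model as supportive. A word saying so would be harmless, but neither the primary conclusion nor the sample size of 33 per arm depends on it.
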